In humans, the energy intake-independent effects of leptin have been assessed in only two studies. A single patient with acquired, generalized lipodystrophy was studied while taking leptin, and during leptin withdrawal, while maintaining constant energy intake²⁹. In this patient, blood glucose did not change during leptin withdrawal, a rise in serum insulin (indicative of worsening insulin resistance) was seen after four days, and a rise in triglycerides after seven days. Although based on a single subject, these data suggest that leptin's effects on both insulin resistance and lipids may be partly independent of energy intake in humans. Liebel's group studied the energy intake-independent effects of leptin in ten healthy subjects following 10% weight loss, a model of relative leptin deficiency¹¹. Subjects in the weight-reduced state were studied before and after five weeks of leptin replacement to pre-weight-loss levels, while maintaining constant energy intake. Leptin replacement resulted in an increase in energy expenditure to pre-weight-loss levels that appeared to be due to changes in skeletal muscle work efficiency, thyroid hormones, and catecholamines. Because these subjects did not have abnormalities of glucose or lipid metabolism, the energy intake-independent effects of leptin on these parameters were not examined.

Subject Eligibility Assessment and Enrollment

Inclusion Criteria

1. Age 14-70 years (children under age 18 will only be enrolled in the leptin-naïve arm of the study [Inclusion criterion 3b, below])
2. Clinically-significant lipodystrophy as summarized below:
 - a. Lipodystrophy identified by the study physician during physical examination as an absence of fat outside the range of normal variation.
 - b. Circulating leptin levels < 12.0 ng/mL in females and < 8.0 ng/mL in males
 - c. Presence of at least one of the following metabolic abnormalities:
 - i. Diabetes as defined by the 2007 American Diabetes Association criteria:
 1. Fasting plasma glucose \geq 126 mg/dL, or
 2. 2-hour plasma glucose \geq 200 mg/dL following a 75 gram 91.75 gm/kg) oral glucose load, or
 3. Diabetic symptoms with a random plasma glucose \geq 200 mg/dL.
 - ii. Fasting insulin $>30 \mu\text{U}/\text{mL}$
 - iii. Fasting hypertriglyceridemia $>200 \text{ mg/dL}$
 3. Either:

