This is an exploratory study of the energy-intake independent effects of leptin initiation and withdrawal in lipodystrophy. Preliminary data are not available to generate estimates of power for each outcome to be tested. The primary comparisons to be tested for each outcome of interest are results at the end of Period 1 versus the end of Period 2, analyzed separately for each group of subjects (leptin-naïve versus leptin treated). Thus, sample size calculations are based on paired, before and after, comparisons within each group of subjects. The data and references used for power calculations are shown in the table, below. Data in the table using the 10% weight loss model are given as percent change from pre-weight loss values, while data from lipodystrophy patients are given as absolute differences between leptin treated and untreated states. All calculations assumed a sample size of 10 and an alpha of 0.05, without correction for multiple comparisons. Because the standard deviations (SDs) of differences between on and off leptin conditions were not reported in publications, the SDs of the difference (used to calculate power for paired comparisons) was estimated in two ways: First, the SDs of differences are calculated by assuming that the SDs of on and off leptin reported in the literature are independent (Power 1 in the table). Second, a “worst-case scenario” was assumed that the SDs on and off leptin in the literature are perfectly positively correlated (Power 2 in the table). The first scenario is the commonly used method, while the second case is the most conservative calculation.

Outcome	Model	Duration of leptin	Off-leptin mean (SD)	On-leptin mean (SD)	Power 1	Power 2
Total energy expenditure ¹¹ (% Δ in kcal/day)	10% wt loss	5 wk	-22% (15.8)	-6% (4.7)	0.92	0.79
Skeletal muscle work efficiency ¹¹ (% Δ in kcal/min expended during exercise vs. at rest)	10% wt loss	5 wk	20% (12.6)	3% (2.5)	0.99	0.97
Resting energy expenditure ²⁴	lipodystrophy	4 mo	35.5 (8.2)	33.6 (6.7)	0.14	0.11
T3 ¹¹ (% Δ)	10% wt loss	5 wk	-9% (6.3)	3% (3.2)	0.99	0.99

T3 ⁴³ (nmol/L)	lipodystrophy	4 mo	124 (37)	114 (26)	0.18	0.13
T4 ¹¹ (% Δ)	10% wt loss	5 wk	-7% (7.9)	-1% (1.3)	0.77	0.66
fT4 ⁴³ (pmol/L)	lipodystrophy	4 mo	1.05 (0.15)	1.03 (0.15)	0.09	0.08
TSH ⁴³ (μU/mL)	lipodystrophy	4 mo	1.37 (0.37)	1.24 (1.1)	0.10	0.09
Norepinephrine ¹¹ (% Δ)	10% wt loss	5 wk	-12% (15.8)	-7% (12.6)	0.19	0.14
Epinephrine ¹¹ (% Δ)	10% wt loss	5 wk	-40% (35)	28% (47)	0.98	0.83

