Sympathetic nervous system tone ¹¹ (% Δ in mean ECG R-R interval after atropine + esmolol vs. atropine alone)	10% wt loss	5 wk	-25% (22.1)	1% (1.6)	0.98	0.97
Liver volume ²⁴ (cm ³)	lipodystrophy	4 mo	3055 (1051)	2433 (763)	0.45	0.29
Total body insulin sensitivity ³¹ (glucose infusion rate during clamp, mg*kg ⁻¹ *min ⁻¹)	lipodystrophy	1 mo	2.5 (0.79)	3.7 (1.1)	0.87	0.63
Total body insulin sensitivity ²⁵ (glucose infusion rate during clamp, mg*kg ⁻¹ *min ⁻¹)	lipodystrophy	4 mo	1.2 (0.35)	5.4 (1.6)	1	1
Hepatic insulin sensitivity ²⁵ (% suppression of endogenous glucose production during clamp)	lipodystrophy	4 mo	40 (10.4)	82 (8.7)	1	1
Fasting glucose ³¹ (mg/dL)	lipodystrophy	7 d	172 (20)	120 (12)	1	0.99
Fasting triglycerides ³¹ (mg/dL)	lipodystrophy	7 d	700 (272)	260 (98)	0.99	0.98
Fasting triglycerides ³¹ (mg/dL)	lipodystrophy	14 d	700 (272)	110 (38)	1	0.99
Rate of lipolysis ²⁵ (glycerol turnover, μmol*kg fat mass ⁻¹ *min ⁻¹)	lipodystrophy	4 mo	78 (36)	25 (7)	0.99	0.99

Based on these calculations, a sample size of 10 subjects in each group (leptin-naïve and leptin-treated) will provide greater than 80% power (in most cases greater than 95%) for the following primary and secondary outcomes:

Glucose Metabolism

1. Total body insulin sensitivity
2. Hepatic insulin sensitivity
3. Fasting plasma glucose

Lipid Metabolism

1. Rate of lipolysis
2. Fasting triglycerides

Energy Expenditure

1. Total energy expenditure
2. Skeletal muscle work efficiency

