Exploratory outcomes for which we anticipate greater than 80% power include epinephrine and sympathetic nervous system tone. Discrepant data exist for the effects of leptin on thyroid function (specifically, T3) based on the model used (lipodystrophy versus 10% weight loss), and this study should help to clarify whether this effect does or does not exist in lipodystrophy. We do not anticipate observing significant changes in resting energy expenditure; however, because this procedure is minimal risk, we feel that it will be important to document negative results for this outcome. Certain outcome measures, such as liver triglyceride (for which liver size was a proxy in the table, above), and insulin sensitivity, appear to progressively change over time with leptin replacement. For these outcomes, a 2 week intervention may be insufficient to observe statistically significant results. For other outcome measures, such as intramyocellular triglyceride, preliminary data on the short-term effects of leptin are not available, but effects, if present, are unlikely to be detectable by two weeks.

Therefore, in addition to obtaining data after 2 weeks of leptin withdrawal or initiation, we will restudy subjects in the leptin-naïve group 6 months (range is 5-9 months) after leptin initiation to look for changes that may not be detectable by 2 weeks.

Because some subjects may not complete the study, or may not have interpretable data for each outcome, we plan to enroll up to 20 subjects in each group in order to have 10 completers per group.

Statistical Methods for Data Analysis

Data will be analyzed separately for the leptin naïve and leptin treated subjects. This is done because the effects of leptin withdrawal after long-term treatment are likely to be different from the effects of leptin initiation after long-term deficiency.

Analysis of Primary Outcomes

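### The claim of more than 80% power for total energy expenditure rests on a 5-week study of healthy weight-reduced people and, on the table's own SDs, fails under a two-sided paired t-test even at the full borrowed effect

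*Combined protocol and SAP*

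**What the plan says.** The Sample Size Justification states that "sample size calculations are based on paired, before and after, comparisons within each group of subjects" and that "All calculations assumed a sample size of 10 and an alpha of 0.05, without correction for multiple comparisons". It gives two power figures per outcome, which differ in how the SD of the within-person change is built from the published on-leptin and off-leptin SDs. It then concludes that 10 subjects per group "will provide greater than 80% power (in most cases greater than 95%) for the following primary and secondary outcomes". Under Energy Expenditure the list names total energy expenditure and skeletal muscle work efficiency. Outcome Measures makes 24-hour total energy expenditure the primary outcome of that domain.

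The table labels both of these rows as the 10% weight-loss model at 5 weeks. The section on energy intake independent effects describes that source as a study "in ten healthy subjects following 10% weight loss, a model of relative leptin deficiency", without abnormal glucose or lipid metabolism. The trial instead requires "Clinically-significant lipodystrophy as summarized below", with low circulating leptin and at least one metabolic abnormality, and its Period 2 lasts 14 days.

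Analysis of Primary Outcomes plans a paired t-test, or a Wilcoxon test if the data are skewed, for a difference between periods. No direction is specified.

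**The concern.** Two things are joined in one unqualified sentence. First, the assumed effect and its SDs come from people who cannot meet inclusion criterion 2, after a treatment period two and a half times as long (35 days against 14). The power table has no total energy expenditure row in lipodystrophy, and the human evidence on energy expenditure in the Introduction comes from weight-reduced and congenitally leptin-deficient people. Second, the figure behind the claim appears to have been calculated for a different test from the one planned.

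What is at stake is how a null result is read. A reader told that the trial had more than 80% power for a primary outcome may take a non-significant change as evidence that leptin does not alter energy expenditure in lipodystrophy. The planning data cannot carry that inference.

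**Working it through.** **Inputs** (power table, Sample Size Justification): n = 10 and alpha = 0.05, sidedness not stated.
- Total energy expenditure: off leptin -22% (SD 15.8), on leptin -6% (SD 4.7), so the difference is 16 points.
- Skeletal muscle work efficiency: off leptin 20% (SD 12.6), on leptin 3% (SD 2.5), so the difference is 17 points.

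**SD of the change, total energy expenditure.**
- Independent: sqrt(15.8² + 4.7²) = sqrt(271.73) = 16.48, standard error 16.48/sqrt(10) = 5.21.
- Summed: 15.8 + 4.7 = 20.5, standard error 6.48.

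**Reproducing the plan's figures.** Use power = Φ(difference/SE - 1.645), a one-sided normal approximation.
- Power 1: 16/5.21 = 3.07, and Φ(1.42) = 0.92 (table 0.92).
- Power 2: 16/6.48 = 2.47, and Φ(0.82) = 0.79 (table 0.79).

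For Power 1, a two-sided normal calculation gives 0.87, a one-sided paired t 0.88 and a two-sided paired t 0.78. Of these methods, only the one-sided normal matches both stated figures. Power 2 matches summed SDs. The perfect positive correlation that the text describes would give an SD of 15.8 - 4.7 = 11.1 and a power above 0.99, so it is not the case that was tabulated.

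**Planned test.** Two-sided paired t, 9 df, critical value 2.262, noncentrality = difference/SE. For total energy expenditure:

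| Share of borrowed effect | Difference | Table's method, independent / summed | Two-sided paired t, independent / summed |
|---|---|---|---|
| 100% | 16 | 0.92 / 0.79 | 0.78 / 0.60 |
| 75% | 12 | 0.74 / 0.58 | 0.54 / 0.38 |
| 50% | 8 | 0.46 / 0.34 | 0.28 / 0.20 |

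The shares are assumptions, because the documents do not say how much of the effect carries over. With 10 completers, the change detectable with 80% power by two-sided paired t is 16.4 points (independent SDs) or 20.4 points (summed SDs), against the 16 assumed.

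**Skeletal muscle work efficiency.** Independent SD sqrt(12.6² + 2.5²) = 12.85, summed SD 15.1. The table's method gives 0.99 / 0.97, as stated. Two-sided paired t gives 0.96 / 0.885. This outcome stays above 80% if the full borrowed effect applies.

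**Sensitivity to correlation (assumed).** If the on- and off-leptin values correlate at 0.5, the SD of the change is sqrt(271.73 - 2 × 0.5 × 15.8 × 4.7) = 14.05, and two-sided paired t power for total energy expenditure at 16 points is 0.89. The plan makes no such assumption.

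**The case against.** Much of the borrowing is in plain view. The plan calls the study exploratory, says preliminary data are lacking for some outcomes, and labels the model in every row. The conclusion is tied to those calculations, and any power figure depends on an assumed effect. The source also has a rationale: of the two human studies of intake-independent effects that the plan cites, it is the only one described as measuring energy expenditure. Lipodystrophy is too rare for the sample to grow much. All of this stands, and it rules out a charge of concealment. It does not rescue a figure that falls below 80% under a two-sided version of the planned test, nor a list that drops the condition. A positive within-person correlation would lift the power, as shown, but the plan's stated figures do not use one.

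Three stronger readings are tempting, and the documents do not support them.
- **Leptin lowers energy expenditure in lipodystrophy, or true power is near 0.14.** The resting row falls from 35.5 to 33.6, and the plan says "We do not anticipate observing significant changes in resting energy expenditure". But resting expenditure is a different outcome. It was measured at 4 months, whereas this trial fixes intake for 14 days; the plan reports that leptin cuts intake by about half and that weight fell by a mean of 2.8 kg over 4 months. A difference of 1.9 against an SD of 10.6 shows no direction. Exercise-related expenditure could also change while resting expenditure does not.
- **Total energy expenditure should be treated as T3 was.** For T3 the plan says "Discrepant data exist for the effects of leptin on thyroid function (specifically, T3) based on the model used", but that compares one outcome in two models. Here there is one model, and the other row is another outcome on another scale.
- **Fasting-glucose power should be limited to the initiation arm.** The support is one case: "In this patient, blood glucose did not change during leptin withdrawal". Insulin and triglycerides did rise in that patient, and other rows also describe leptin replacement, so singling out glucose is arbitrary.

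**Conclusion.** The concern holds for the unqualified power claim. For total energy expenditure, power at the full borrowed effect is 0.78 with independent SDs and 0.60 with summed SDs, not more than 80%. The shortfall is small in the first case and clear in the second. These figures assume a two-sided 5% paired t-test, 10 completers and the table's SDs; the plan gives no sidedness, but it plans to test for any difference. If the effect in lipodystrophy at 14 days is smaller than in weight-reduced people at 5 weeks, power falls quickly, to 0.54 at three quarters and 0.28 at one half. Skeletal muscle work efficiency keeps its place on the list, but only on condition that the borrowed effect applies. Nothing here establishes the true power in lipodystrophy, because the documents hold no data from which to derive it.

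**What to change.** In the Sample Size Justification:
- Remove total energy expenditure from the list of outcomes with more than 80% power.
- Restate its power as about 0.78 (0.60 under the conservative SD) by two-sided paired t-test with 10 completers, conditional on the weight-loss-model effect applying in lipodystrophy.
- Keep skeletal muscle work efficiency on the list with the same condition, at 0.96 (0.885 under the conservative SD).

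In Analysis of Primary Outcomes, add that a non-significant change in total energy expenditure will be reported with its confidence interval and not as evidence of no effect.

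The cost is a less favourable stated power for one primary outcome. Patients, procedures and sample size do not change.

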Lipodystrophies, in which there is partial or complete absence of adipose tissue (and hence, adipokines such as leptin), represent another model for understanding the actions of leptin in a state of deficiency and replacement. Unlike patients with congenital leptin deficiency, patients with lipodystrophy are non-obese, but have more extreme manifestations of the metabolic syndrome due to factors such as ectopic lipid storage^{22,23}. Leptin replacement in lipodystrophy reduces food intake^{24,25} and ameliorates most metabolic abnormalities, including insulin resistance^{25,27} and diabetes^{26,28,29}, hypertriglyceridemia^{27,29}, and hepatic steatosis^{25,30}. Based on data derived largely from studies conducted in the intramural research program of the NIDDK, the FDA approved metreleptin (recombinant methionyl leptin) for the treatment of generalized lipodystrophy in February, 2014; however, leptin remains an experimental therapy in other forms of lipodystrophy, including partial lipodystrophy.

Limited information is available about the time course of leptin's effects in lipodystrophy. In seven patients with generalized lipodystrophy, declines in glucose and triglyceride levels reached statistical significance by 7 days after leptin initiation³¹. In these subjects, non-significant increases in insulin sensitivity (measured using the hyperinsulinemic, euglycemic clamp) were seen one month after starting leptin, and significant increases after 2 months.

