More detailed mechanistic studies of leptin's effects on glucose and lipid metabolism after 3-8 months have been performed on three patients with lipodystrophy (one acquired generalized and two congenital generalized)²⁵. Using stable isotope infusions in combination with the hyperinsulinemic, euglycemic clamp, these subjects in the leptin deficient state were shown to have elevated hepatic glucose production and severe hepatic insulin resistance compared to healthy controls. After leptin replacement for 3-8 months, hepatic insulin resistance decreased to nearly that of controls, and insulin-stimulated glucose disposal doubled. These changes were associated with an 86% reduction in hepatic triglyceride content and a 33% reduction in muscle triglyceride, suggesting that reduction in ectopic lipid may have contributed to the improvements in insulin sensitivity. Non-significant decreases in glycerol turnover were also observed following leptin treatment, suggesting that leptin increased lipolysis in any existing adipose tissue or within ectopic lipid stores. In a single subject, a 30% reduction in muscle fatty acyl CoA levels was observed after leptin replacement, offering support for the hypothesis that these compounds contribute to insulin resistance by interfering with insulin receptor substrate-1 (IRS-1) tyrosine phosphorylation, a key step in the insulin signaling cascade. In summary, leptin appears to improve plasma glucose and triglycerides within 1 week, while improvements in insulin sensitivity may be detectable by one month, with continued improvement thereafter, and changes in ectopic lipid storage may not be detectable for several months after leptin initiation.

The effect of leptin on lipid metabolism has also been examined in a randomized, controlled trial of leptin for 4 months in 17 men with HIV associated lipodystrophy³². In this trial, the authors did not find any effects of leptin treatment on lipid metabolism, including fasting triglycerides, rates of lipolysis, and fatty acid oxidation. This suggests that there may be differences in the effect of leptin on lipid metabolism in HIV patients versus the non-HIV infected population studied at NIH. These differences may be related to the severity of the phenotype (typically milder in HIV) or to the doses of leptin used in the HIV study (0.02-0.04 mg/kg/day, which is 25-50% of the lowest doses used in NIH studies).

Energy intake independent effects of leptin

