Measurements in each of the primary outcomes will be analyzed using the paired t-test (for normally distributed variables) or Wilcoxon paired test (for skewed variables) to test if there is any significant difference between the two study periods (on and off leptin) for each group (leptin naïve and leptin treated), respectively. In addition, mixed models incorporating baseline (pre-diet) parameters as covariates will be used to adjust for any effects of the inpatient, metabolic diet, independent of leptin's effects. For variables with more than 2 measurements during Period 2, repeated measure linear models (Mixed model or GLM) will be used to study the time effect, using pooled data from the 2 periods. Potential covariates to be explored in the model include: Age, sex, race, percent body fat, lean mass, body weight, type of lipodystrophy, and endogenous leptin level. To account for any deviation from the isocaloric protocol diet, actual caloric intake will be included as a covariate in mixed model analyses.

Additional correlations between variables within and between each of the major outcome categories (glucose metabolism, lipid metabolism, and energy expenditure) will be analyzed using either Pearson's correlation or simple linear regressions. These include the following:

1. Association between change in total body insulin sensitivity and changes in hepatic insulin sensitivity, fasting plasma glucose, and C-peptide
2. Association between change in rate of lipolysis, and changes in fasting triglycerides and fatty acid turnover
3. Association between insulin sensitivity and ectopic lipid stores, and rates of lipolysis and fatty acid turnover
4. Association between change in total energy expenditure and changes in resting energy expenditure, skeletal muscle work efficiency, spontaneous physical activity, thyroid function, catecholamines, and cardiac autonomic nervous system tone.

Analysis of Secondary and Exploratory Outcomes

Methods for analysis of secondary outcomes will be similar to those for primary outcomes. In addition, we will perform analysis to study the following associations between categories of outcome measures:

1. Association between the Ectopic Lipid measurements with Glucose and Lipid measurements
2. Association between the Endocrine measurements with Energy Expenditure measurements

Analysis of long-term data

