SAEs, whether related or not related to study drug, (including pregnancies) must be reported to Aegerion Pharmaceuticals on an SAE Report Form or similar form (e.g. CIOMS, MedWatch) and submitted as soon as possible but not more than 7 calendar days in the event of a death or a life-threatening event or in 15 calendar days for all other SAEs. SAE reports within 7 calendar days are to be transmitted via email:

SAE Email Address: [contact] and [contact]

If only limited information is initially available, follow-up reports are required. (Note: Follow-up SAE reports should include the same investigator term(s) initially reported). If an ongoing SAE changes in its intensity or relationship to study drug or if new information becomes available, a follow-up SAE report should be sent to the Aegerion Pharmaceuticals (or designee) using the same procedure used for transmitting the initial SAE report. All SAEs should be followed to resolution or stabilization.

Per NIH HRPP SOP 16, all serious adverse events will be reported to the NIDDK/NIAMS IRB at the time of annual review. The PI will report all deaths (that are not Unanticipated Problems) to the NIDDK CD and NIDDK/NIAMS IRB as soon as possible, but not more than 7 days after the PI first learns of the event, unless otherwise specified by the NIDDK CD and documented in the protocol.

Deaths

Per NIH HRPP SOP 16, the PI will report all deaths (that are not Unanticipated Problems) to the NIDDK Clinical Director and the NIDDK/NIAMS IRB as soon as possible, but not more than 7 days after the PI first learns of the event, unless otherwise specified by the NIDDK CD and documented in the protocol.

Rationale for Subject Selection

Subjects eligible for this study include mature adolescents and non-elderly adults with lipodystrophy. All subtypes of lipodystrophy (i.e. generalized, partial, acquired, and congenital) will be eligible. Although restricting the study to one or two lipodystrophy subtypes (such as the most severe forms: acquired and congenital generalized) would likely give greater homogeneity in the patient population, such restrictions would dramatically decrease feasibility in this extremely rare condition. Because each subject will be compared to him/herself in this within-subjects design, the effects of inter-subject heterogeneity will be less important.

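### Power above 80% for the glucose, insulin-sensitivity and triglyceride outcomes comes only from generalized lipodystrophy and is not shown for the all-subtype trial; total body insulin sensitivity is the fragile case

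*Combined protocol and SAP*

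**What the plan says.** The Sample Size Justification tabulates power for paired before-and-after comparisons within each group: "All calculations assumed a sample size of 10 and an alpha of 0.05, without correction for multiple comparisons". From the table it concludes that 10 per group "will provide greater than 80% power (in most cases greater than 95%) for the following primary and secondary outcomes", and the list that follows includes total body insulin sensitivity, hepatic insulin sensitivity, fasting glucose and fasting triglycerides.

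Those rows are labelled only as lipodystrophy and cite two references, 31 and 25. The Introduction (Leptin in lipodystrophy) describes their patients. For reference 31: "In seven patients with generalized lipodystrophy, declines in glucose and triglyceride levels reached statistical significance by 7 days after leptin initiation". For reference 25: "three patients with lipodystrophy (one acquired generalized and two congenital generalized".

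The trial population is wider. Under Rationale for Subject Selection, "All subtypes of lipodystrophy (i.e. generalized, partial, acquired, and congenital) will be eligible". Inclusion criterion 2c asks for "Presence of at least one of the following metabolic abnormalities", the options being diabetes, fasting insulin above 30 µU/mL or fasting triglycerides above 200 mg/dL. Criterion 2b allows leptin levels up to 12.0 ng/mL in females and 8.0 ng/mL in males. The Rationale concedes that restricting subtype would give a more homogeneous sample, and answers: "Because each subject will be compared to him/herself in this within-subjects design, the effects of inter-subject heterogeneity will be less important".

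**The concern.** Every effect size behind the listed glucose, insulin-sensitivity and triglyceride power comes from generalized disease, while the enrolled sample may be a mixture. No power is given for a mixture.

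The within-subject argument does not close the gap. Pairing cancels a subject's own level. If subtypes differ in how much they change, that difference stays in the paired difference: weak responders lower its mean, and the spread of responses adds to its SD. Both reduce power.

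What is at stake is the reading of a null result. If an outcome is believed to have more than 80% power, a non-significant change invites the conclusion that leptin has no intake-independent effect. A single pooled change may also describe neither generalized nor partial disease well.

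**Working it through.** **Inputs.** From the Sample Size Justification: n = 10, alpha 0.05, and the tabled off- and on-leptin means and SDs. From the Introduction: the source populations. Assumed, because the documents give neither: the share f of subjects with the full planned effect d, and the fraction r of that effect shown by the rest.

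**Step 1: reproduce the plan's figure.** Power 1 treats the two SDs as independent, so SDdiff = √(SDoff² + SDon²). The table matches power = Φ(d√10/SDdiff − 1.645), a one-sided normal formula, although sidedness is not stated. For total body insulin sensitivity at 1 month, 2.5 (0.79) against 3.7 (1.1):
- d = 1.2 and SDdiff = √(0.624 + 1.210) = 1.354
- d√10/SDdiff = 2.80
- power = Φ(1.157) = 0.88, against 0.87 in the table

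A two-sided paired t-test (noncentral t, 9 df) on the same inputs gives 0.70. The tabled Power 2 of 0.63 reproduces, at 0.64, with SDdiff = 0.79 + 1.1 = 1.89.

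**Step 2: margin in that row.** 80% power needs d√10/SDdiff = 1.645 + 0.842 = 2.487. The share of the planned effect required is 2.487/2.802 = 0.89, a mean change of about 1.06 rather than 1.2 mg/kg/min. The corresponding shares are 0.25 for hepatic sensitivity and 0.35 for fasting glucose.

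**Step 3: mixed response.** With share f at the full effect and the rest at r times it:
- mean = d[f + (1 − f)r]
- SD = √(SDdiff² + d² f(1 − f)(1 − r)²)

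For 1-month insulin sensitivity with f = 0.5:
- r = 0.5: mean 0.90, SD √(1.834 + 0.090) = 1.387, power Φ(2.052 − 1.645) = 0.66
- r = 0.25: mean 0.75, SD √(1.834 + 0.2025) = 1.427, power Φ(1.662 − 1.645) = 0.51

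All rows, on the plan's formula, with the two-sided paired t-test in brackets:

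| Row | d | SDdiff | All full effect | Half at 50% | Half at 25% | Half at 0 |
|---|---|---|---|---|---|---|
| Total body insulin sensitivity, 1 mo | 1.2 | 1.35 | 0.88 (0.70) | 0.66 (0.45) | 0.51 (0.32) | 0.36 (0.21) |
| Total body insulin sensitivity, 4 mo | 4.2 | 1.64 | 1.00 (1.00) | 1.00 (0.99) | 0.98 (0.90) | 0.80 (0.60) |
| Hepatic insulin sensitivity, 4 mo | 42 | 13.6 | 1.00 (1.00) | 1.00 (1.00) | 0.99 (0.94) | 0.84 (0.66) |
| Fasting glucose, 7 d | 52 | 23.3 | 1.00 (1.00) | 1.00 (0.98) | 0.96 (0.85) | 0.76 (0.56) |
| Triglycerides, 14 d | 590 | 275 | 1.00 (1.00) | 1.00 (0.98) | 0.95 (0.84) | 0.75 (0.54) |
| Triglycerides, 7 d | 440 | 289 | 1.00 (0.99) | 0.96 (0.85) | 0.83 (0.64) | 0.61 (0.40) |

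**Step 4: what entry allows.** A subject can qualify on fasting insulin alone with triglycerides at or below 200 mg/dL. Even a fall to zero would then be at most 200/590 = 0.34 of the planned 14-day change, or 200/440 = 0.45 of the 7-day change. Reduced response is therefore built into the criteria for triglycerides.

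**Limit of the calculation.** The mixtures give low responders the full SDdiff. For triglycerides this is pessimistic, since a subject starting near 200 cannot vary by 289. If the SD of the low responders shrinks with their effect, simulation of the 7-day half/quarter case gives about 0.93 for the two-sided t-test, against 0.64 above.

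**The case against.** A reader might infer that the stated power is wrong for these outcomes as a group, or that the planning off-leptin state occurs only in generalized disease. The documents support neither. They say who was studied, not that other subtypes lack that state. The Benefits section reports clinically important improvement in partial lipodystrophy with significant metabolic disease, without figures. In the half/quarter case every row except 1-month insulin sensitivity stays above 80% on the plan's formula, including the 4-month clamp row and the 14-day triglyceride row, which matches the length of Period 2.

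The entry criteria also say little about the one fragile outcome. A subject admitted on fasting insulin alone is insulin resistant, and a normal glucose or triglyceride level does not show that the clamp response will be small.

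The plan has caveats too. It calls itself exploratory, prints a Power 2 of 0.63 for the 1-month clamp row, warns that two weeks may be too short for insulin sensitivity, and lists type of lipodystrophy as a potential covariate. These stand, and they limit the point. None of them concerns subtype in the power claim, however. The closing list still gives total body insulin sensitivity more than 80% power without qualification, and no estimate by type is planned.

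**Conclusion.** The point holds in a limited form: the power for these outcomes is not shown for the population the trial admits. It is fragile for total body insulin sensitivity. Of the two clamp rows, the 1-month row is nearer to the 14-day intervention, and it loses 80% power with about an 11% shortfall in mean effect. By two-sided paired t-test it is below 80% (0.70) before any dilution. Hepatic sensitivity, fasting glucose and 14-day triglycerides have wide reserve. They come near or below 80% on the plan's formula only under strong dilution: 0.84, 0.76 and 0.75 if half the subjects do not respond at all.

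No single corrected power can be given. The subtype mix and response ratios are assumptions, and the triglyceride figures also assume that low responders keep the full SD.

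**What to change.** 1. In the Sample Size Justification, state that the glucose, insulin-sensitivity and triglyceride figures come from generalized lipodystrophy. For total body insulin sensitivity, replace the unqualified claim of more than 80% with the range: 0.88 undiluted, 0.66 and 0.51 in the two mixed cases on the plan's formula, or 0.70, 0.45 and 0.32 by two-sided paired t-test. Label the mixes as assumptions and note that the other outcomes are fairly robust.
2. In Rationale for Subject Selection, say that pairing removes heterogeneity of level, whereas heterogeneity of response lowers the mean change and raises the SD of the paired difference.
3. In Analysis of Primary Outcomes, report the change with its 95% confidence interval by type (generalized, partial) beside the pooled estimate, labelled descriptive. Treat any type-by-period term as exploratory.

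The cost is wording plus a summary of data already collected; eligibility, sample size and procedures stay as they are. The stated power becomes less favourable, and with about 10 completers per group the by-type intervals will be wide.
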